6.2.2 Disease Progression

Investigator-determined disease progression will be collected as an exploratory endpoint at the end of treatment and presented in data listings for the enrolled analysis set. Clinical assessment and radiologically confirmed outcomes recorded on the CRF per the standard of care at the site. Progression (clinical or radiological) and date of procedure (date on which radiological procedures were performed or date of clinical assessment) will be listed.

6.3 Safety

Unless otherwise specified, safety analyses will be performed on the SAF. Data will be presented by overall and listings by parent study.

6.3.1 Primary Safety Outcomes

The primary safety outcomes include incidence of TEAEs and TESAE, as well as drug-related TEAEs and TESAEs. Their analysis is described in Section 6.3.3 below.

6.3.2 Study Drug Exposure

Exposure to anetumab ravidansine will be summarized in the SAF, including number of cycles and duration of treatment during the rollover study. Exposure to combination therapies that continue from the parent study will be presented in data listings only.

Duration of treatment is defined as (last dose date-first dose date) +1.

6.3.3 Adverse Events

Treatment-emergent AEs (TEAEs)

In this study, treatment-emergent adverse events are defined as adverse events starting or worsening during the treatment period. The treatment period extends from the first date of treatment in this study until the safety follow-up (30 days after the last administration of study treatment).

Coding and grading of TEAEs

TEAEs will be coded using the latest MedDRA version, and toxicity will be graded using NCI-CTCAE v5.0. Corneal epitheliopathy events (classified as corneal disorders) will be graded according to the Bayer Grading System.

Study drug-related AEs

AEs will be reported as study drug-related if they are documented by the investigator as related to any study drug.

AEs of Special Interest (AESIs)

Adverse events of special interest include any corneal epitheliopathy and infusion-related reactions (IRRs).

Reporting of TEAEs

The incidence of TEAEs and TESAEs, as well as drug-related TEAEs and TESAEs will be summarized in descriptive summary tables (number and percentage of participants) by latest MedDRA version SOC and preferred term (PT) and by worst grade for the following:

- Overview of TEAEs
- TEAEs
- TEAEs in descending order of frequency by Preferred Term (PT)
- Study drug-related TEAEs
- Study drug-related TEAEs in descending order of frequency by PT
- TESAEs
- TESAEs in descending order of frequency by PT
- Study drug-related TESAEs
- Study drug-related TESAEs in descending order of frequency by PT
- TE(S)AEs leading to permanent discontinuation
- TE(S)AEs leading to dose interruption

- TE(S)AEs leading to dose reduction
- Overview AEs of special interest

All AEs, TEAEs, TESAEs, and TEAEs leading to discontinuation of study drug will be presented in separate listings. Listings will be provided in all enrolled participants. AEs of special interest will be included in summary tables of AEs and will be presented in data listings.

A summary of deaths during the treatment period and following 30 days after treatment end in this study will be reported for the safety set. A listing of all deaths at any time during the study will be provided in all enrolled participants.

6.3.4 **Laboratory assessments**

The following laboratory parameters will be summarized in all treated participants:

- Hematology: platelet count, red blood cell count (RBC), hemoglobin, hematocrit, white blood cell count (WBC) with differential
- Clinical chemistry: aspartate aminotransferase (AST), alanine aminotransferase (ALT), total bilirubin, creatinine
- Serum pregnancy test results will be reported through listings

The clinically relevant laboratory parameter changes occurring during the study were to be reported as adverse events (Section 8.2.3 of the clinical study protocol).

For purposes of the safety analysis, only numerical laboratory values (no clinical assessments) will be used for providing severity ranges for the laboratory data. Ranges are described in Bayer internal documentation [4]. Laboratory toxicities assigned by the investigator or reported as AEs will be documented in the AE CRFs and reported in AE tables and listings; these toxicities may include clinical assessments. The incidence of laboratory toxicities will be summarized in frequency tables.

For laboratory assessments with normal ranges, low/normal/high status will be reported in listings as applicable.

6.3.5 **Other Safety Measures**

In addition, all laboratory assessments, vital signs, and ophthalmologic examination results will be presented in data listings. Listings will be reported in all enrolled participants.

7. **Document history and changes in the planned statistical analysis**

SAP version 1.0, dated 23 MAY 2019.

8. **References**

Statistical Analysis Plan

BAY 94-9343/20322

Page: 10 of 10

3. Collett, D. *Modelling Survival Data in Medical Research: Third Edition*. CRC Press. (2015) p. 29.
4. Handling Laboratory Findings in Bayer Oncology Clinical Trials (Internal) 15 FEB 2019

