AE/SAE review	X	X	X		Any (S)AE in the parent study which is ongoing at the time of signing informed consent for the rollover study, must be reported as (S)AE in the rollover study and re-graded to CTCAE V5.0. Further follow-up and documentation should occur in the rollover study.
Concomitant medication review	X	X	X		For on-treatment participants: documentation of concomitant medication ongoing at the time of parent study closure, and any new concomitant medication started after signing of ICF
Survival status and new or ongoing anti-cancer treatment				X	
Collect local tumor response information		X			Collect local imaging information (assessment date and outcome) obtained as per standard of care
IxRS	X	X	X		Inform IxRS of end of Treatment in ROS as soon as possible, at the latest at Safety FU visit

Abbreviations: AE = Adverse event; ALT = Alanine aminotransferase; AST = Aspartate aminotransferase; C1D1 = Cycle 1 Day 1; FU = Follow-up; ICF = Informed consent form; IxRS = Interactive voice/web response system; ROS = Rollover study; SAE = Serious adverse event

- The treating investigator should ensure a seamless transition without a change in the treatment schedule. Any treatment interruption for medical reasons between last administration in the parent study and first administration in this study should not exceed 42 consecutive days.
- During the last planned visit in the parent study, ROS eligibility criteria will be reviewed and the participants may sign informed consent for the rollover study. After signature of ROS ICF, any further procedures/events including C1D1 drug administration are part of the ROS and will be documented there.

2. Introduction

There are currently multiple ongoing anetumab ravidansine clinical studies and some of the participants in these studies will still be ongoing at the time when their clinical study is planned to be closed. The intention of this rollover study is to enable participants, who are still benefiting from treatment, to continue to receive treatment in the rollover clinical study instead of parent study. For applicable studies, patients in active and/or long-term follow up will also be enrolled in this rollover study for continued follow up.

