5.1 Inclusion Criteria

Inclusion Criteria

Participants are eligible to be included in the study only if all of the following criteria apply:

- Participants ongoing in an applicable Bayer-sponsored anetumab raptansine parent study at the time of its planned study closure.
- For on-treatment participants: participant is eligible to receive the next dose of study intervention per the parent study protocol.

- For on-treatment participants: any ongoing adverse events that require temporary treatment interruption must be resolved to baseline grade or assessed as stable and not requiring further treatment interruption. For applicable studies: should treatment be permanently interrupted in the parent study, participants may be enrolled in the follow-up portion of the rollover study.
- Women of childbearing potential and men with reproductive potential must be willing to continue practicing acceptable methods of birth control during the study treatment and until 6 months after stopping study treatment. Genetic consultation is recommended if the participant wishes to have children after ending treatment. Contraceptive use by men or women should be consistent with local regulations regarding the methods of contraception for those participating in clinical studies. The investigator or a designated associate is requested to advise the participant how to achieve highly effective birth control. Highly effective (failure rate of less than 1% per year) contraception methods include:
 - Combined (estrogen and progesterone containing: oral, intravaginal, transdermal) and progesterone-only (oral, injectable, implantable) hormonal contraception associated with inhibition of ovulation.
 - Intrauterine device (IUD) or intrauterine hormone-releasing system (IUS).
 - Bilateral tubal occlusion or vasectomized partner (provided that partner is the sole sexual partner and has received medical assessment of the surgical success).
 - Sexual abstinence (reliability to be evaluated in relation to the duration of the clinical trial and the preferred and usual lifestyle of the participant).

Male participants with a female partner of childbearing potential must use a condom and ensure that an additional form of contraception is also used during treatment and until 6 months after last study drug administration.

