Anetumab ravtansine ^c	No change	No change	Keep treatment dose level and schedule if the ophthalmological exam can be performed as needed; otherwise consider dose reduction by -1 dose level without dose schedule change at the discretion of investigator in consultation with ophthalmologist	1) Decrease dose to -1 dose level (or -2 dose level if event does not resolve to Grade ≤ 2 at the -1 dose level within 21 days) 2) Re-start at the original dose level if the first Grade 3 event resolves to Grade ≤ 2 within 21 days and does not recur 3) If not resolved within 21 days continue at reduced -1 dose level (or -2 dose level) ^d	Discontinue treatment

MTD = Maximum tolerated dose; SPK = Superficial punctate keratitis

a Oxford Schema must be used for grading SPK from stage 0 to V (see Appendix 10.6).

b Other remedial therapies for corneal epitheliopathy may be added or substituted at investigator's discretion or according to the institutional standards.

c Treatment decisions are based on corneal epitheliopathy only, not on visual acuity changes

d If the MTD of anetumab ravtansine is set at 5.5 mg/kg for either cholangiocarcinoma and/or pancreatic adenocarcinoma, only one dose reduction to 4.5 mg/kg will be allowed. If the MTD of anetumab ravtansine is set at 4.5 mg/kg for either cholangiocarcinoma and/or pancreatic adenocarcinoma, no dose reductions will be allowed; toxicities requiring dose reductions in this instance will result in permanent discontinuation of anetumab ravtansine.

Table 6-2: Bayer classification of visual acuity changes

	Grade 0	Grade 1	Grade 2	Grade 3	Grade 4
Visual acuity	No findings, no reporting from the patient	Symptomatic visual acuity loss < 3 lines (ETDRS equivalent ^a)	Visual acuity loss ≥ 3 lines, but < 6 lines (ETDRS equivalent ^a)	Visual acuity loss ≥ 6 lines (ETDRS equivalent ^a)	Visual acuity loss ≥ 6 lines (ETDRS equivalent ^a) leading to blindness

ETDRS = Early Treatment Diabetic Retinopathy Study

^a In the ETDRS chart, each loss of 3 lines corresponds to halving the visual acuity. In other charts, an equivalent amount of visual acuity loss must be reached in order to meet this threshold.

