8.3.1 Time Period and Frequency for Collecting AE and SAE Information

All (S)AEs will be collected from the signing of the informed consent form (ICF) until the follow-up visit at the time points specified in the SoA (Section 1.3).

For on-treatment participants, the following must be documented in the medical history section of the eCRF: prior clinical and surgical conditions and also relevant events that occurred during the course of parent study. Relevant events are defined as AE's leading to dose reduction, interruption/delay.

Any AE/SAE in the parent study which is ongoing at the time of signing informed consent for the rollover study must be reported in a new CRF page on the rollover study, per CTCAE V5.0, or Bayer Grading system for corneal epitheliopathy events. Further follow-up of these events will occur in the rollover study.

Medical occurrences that begin before the start of study intervention in this study but after obtaining informed consent will be recorded on the AE section of the case report form (CRF).

Medical occurrences that started before but deteriorated after obtaining informed consent will be recorded as adverse events.

All SAEs will be recorded and reported to the sponsor or designee immediately and under no circumstance should this exceed 24 hours, as indicated in Appendix 3 (Section 10.3). The investigator will submit any updated SAE data to the sponsor within 24 hours of it being available.

Investigators are not obligated to actively seek AE or SAE after the safety follow-up visit. However, if the investigator learns of any SAE, including a death, at any time after a participant has been discharged from the study, and he/she considers the event to be

reasonably related to the study intervention or study participation, the investigator must promptly notify the sponsor.

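### AEs carried over from the parent study that persist without worsening are excluded from the three action-taken tables, even when they cause a dose reduction, interruption or discontinuation in the rollover study

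*SAP*

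**What the plan says.** **Definition.** In SAP 6.3.3, "treatment-emergent adverse events are defined as adverse events starting or worsening during the treatment period". The clock is tied to this study: "The treatment period extends from the first date of treatment in this study until the safety follow-up".

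**Tables.** The same section plans three tables by action taken, all limited to treatment-emergent events: "TE(S)AEs leading to permanent discontinuation", "TE(S)AEs leading to dose interruption", and the matching table for dose reduction.

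**What is collected.** Under the Schedule of Activities (Protocol 1.3), an AE or SAE still ongoing at rollover consent "must be reported as (S)AE in the rollover study and re-graded to CTCAE V5.0". Protocol 8.3.1 repeats this: the event "must be reported in a new CRF page on the rollover study, per CTCAE V5.0", or by the Bayer grading system for corneal epitheliopathy, and is followed up in the rollover study.

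**Who may enter.** Protocol 5.1 admits on-treatment participants whose earlier interrupting AE has returned to baseline grade or is "assessed as stable and not requiring further treatment interruption".

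**Protocol 6.6.** This section has its own definition of a TE(S)AE requiring dose modification: an AE related to study intervention, at whatever point in the study it happens. It does not require the event to start or worsen after the first rollover dose.

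**The concern.** The study exists to gather long-term safety information on people already exposed to the drug. In that setting, a toxicity that started earlier, does not go away and finally limits treatment is one of the most informative things to count. The plan collects such an event and the reason for the dose change, but the start-or-worsen rule removes it from the tables meant to show which AEs led to dose changes. The reported action rates would then be too low, and lowest for persistent toxicity. An AE-driven stop could also appear in disposition with no matching row in the AE discontinuation table and no explanation for the difference.

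**Working it through.** The plan states no figure to reproduce, so the check follows one event through every planned output: an AE that began in the parent study, is ongoing at rollover consent, stays at the same grade, and leads to a dose action after the first rollover dose.

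**Step 1. Is it a TEAE?** It did not start in the rollover treatment period and did not worsen in it. Under SAP 6.3.3 it is not.

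**Step 2. Where is it counted?**

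| Planned output | Event or action counted? |
|---|---|
| TEAE, TESAE and drug-related tables (SAP 6.3.3) | No |
| Discontinuation, interruption and reduction tables (SAP 6.3.3) | No under the SAP definition; arguably yes under Protocol 6.6 if related |
| AESI overview (SAP 6.3.3) | Unclear: its title does not say treatment-emergent, but the sentence introducing the list does; no breakdown by action is specified |
| Disposition (SAP 6.1.1) | A discontinuation is counted by reason, without the AE term; reductions and interruptions are not covered |
| Exposure (SAP 6.3.2) | Names cycles and duration only; no dose changes |
| Laboratory toxicity tables (SAP 6.3.4) | The value is counted if it is a laboratory abnormality; the action is not |
| Listing of TEAEs leading to discontinuation (SAP 6.3.3) | No |
| Listing of all AEs (SAP 6.3.3) | Yes |

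So a reduction or interruption reaches no planned summary, a discontinuation reaches only disposition, and the all-AE listing is the one AE output sure to show the event.

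**Step 3. Can an action follow without a rise in grade?** Yes, on the protocol's own text. In Protocol Table 6-1 (Grade 3 column, anetumab ravtansine row) a further dose step applies "if event does not resolve to Grade ≤ 2 at the -1 dose level within 21 days". The trigger is failure to resolve. The Grade 2 column also allows a reduction to be considered when the eye examinations cannot be done as needed, again without worsening. More generally, Protocol 4.1 ends treatment for unacceptable toxicity without asking for an increase in grade.

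**Step 4. Do the two documents agree?** No. SAP 6.3.3 requires onset or worsening after the first rollover dose. Protocol 6.6 requires relatedness and occurrence during the study. A related carried-over AE is excluded by the first and arguably included by the second. The SAP uses the TE(S)AE notation, which is also the protocol's, only in the three action-table titles, so two programmers could build different tables.

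**Step 5. Size.** Protocol 9.2 calls the number of participants unpredictable, and neither document gives an event rate. With N participants in the safety analysis set, one affected participant not already counted in a given table changes its percentage by 1/N:

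- assumed N = 20: 1/20 = 5.0 percentage points
- assumed N = 40: 1/40 = 2.5 percentage points

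This is a ceiling per participant. The tables count participants, so someone who also has a qualifying TEAE with the same action is already in the table and adds nothing.

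**The case against.** The strongest reply is that Protocol 6.6 may already bring these events in. The three table titles use its term, and its definition has no start-or-worsen condition. That is a fair reading, but it does not settle the matter. The SAP states its own TEAE definition for this study, the protocol's verb could refer to onset, and an unrelated AE that led to an action would still be left out. What stands is that the two texts are unreconciled.

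Second, the corneal example is narrow. In the Grade 3 column, non-resolution leads to a further or continued reduction, not to an interruption or a stop. The Grade 4 column is where treatment ends, and moving from Grade 3 to Grade 4 is worsening, hence a TEAE. The first dose step for a parent-study event would normally fall in the parent study, and the entry criteria thin out such cases. This stands: the example directly supports the reduction table only, and the documents do not show how often the case would arise.

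A reader might also infer three stronger claims, none of which the documents support:

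- That these events enter no summary at all. Disposition counts a discontinuation by reason, the laboratory tables count abnormal values, and the AESI overview may include a carried-over corneal event.
- That neither study's action tables would count the action. The parent-study analysis plans are not available here. Protocol section 9 allows pooling with parent data, although only as an option, and the SAP plans no pooled AE table.
- That a given share of AE-driven actions is missed. Nothing in either document gives such a share.

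**Conclusion.** The concern holds for the three action-taken tables. Under SAP 6.3.3, a carried-over AE that persists without worsening is excluded from the TEAE tables and from all three action tables, even when it causes the action in the rollover study. SAP 6.3.3 and Protocol 6.6 also give different rules for what counts.

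The exclusion and the conflict follow from the wording and need no numerical assumption. The size is unknown: the per-participant ceilings in the working rest on assumed N, and the number of such participants cannot be derived. The primary TEAE and TESAE tables are not at fault, since counting only new or worsened events is what a treatment-emergent incidence is meant to do.

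**What to change.** In SAP 6.3.3:

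1. Base the discontinuation, interruption and reduction tables on all AEs recorded in the rollover study that led to the action on or after the first rollover dose, whatever their onset. Show treatment-emergent and carried-over events in separate columns, with a total that counts each participant once.
2. Reconcile the wording with Protocol 6.6, so that one definition governs these tables.
3. State whether the AESI overview is limited to TEAEs.
4. Name the reference grade for worsening: the CTCAE v5.0 or Bayer re-grade at rollover entry. Without this, the required re-grading could by itself look like a change in severity.

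Leave the TEAE definition and the primary TEAE tables unchanged. A further table of AEs ongoing at the first rollover dose would be useful but is optional.

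**Cost.** SAP wording and some programming. Protocol 6.4 puts the reasons for dose changes on the CRF and Protocol 8.3.1 puts the carried-over AE there, but neither states that an action date is held with each AE. The action date therefore has to be linked to the AE, probably through the dosing records. The reported action rates may also rise.
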